5.6 Supportive Care Guidelines

 Subjects should receive appropriate supportive care measures as deemed necessary by the treating Investigator including but not limited to the items outlined below.

5.6.1 Cytokine Release Symptoms

Cytokine Release Symptoms is a constellation of inflammatory symptoms resulting from cytokine elevations associated with T cell engagement and proliferation. Symptoms related to cytokine release may include constitutional symptoms such as fever, chills, rigors, headache, nausea, vomiting, rash tachycardia, hypotension, , and shortness of breath which usually presents several hours after the infusion and may last for up to 24 hours. These symptoms are caused by an increase in cytokines such as TNF α , IFN γ and

IL-6, all of which have been shown to occur after ADXS11-001 administration, resulting from the body's immune response to the therapy. Although, symptoms are often grade 1-2 and transient, resolving with symptomatic management within 30 minutes-1 hour, in rare instances (~1%) grade 3-4 hypotension has been seen. Therefore, close monitoring of blood pressure is strongly recommended at baseline, and during the post-infusion period. Increased levels of IL-6, has been strongly associated with capillary leak which manifests as hypotension due to the cytokines involved. We have observed elevated IL-6 levels after infusion of ADXS11-001, with peak levels occurring 2-4 hours after infusion. Emerging evidence indicates that IL-6 antagonists, such as Tocilizumab, has demonstrated good results in treating cytokine-induced hypotension [19-22] and is therefore recommended for cases of severe hypotension refractory to supportive care (e.g. fluids and/or pressors).

The management of cytokine release symptoms and guidelines for subsequent treatment for patients who have experienced these adverse events are shown in [Table 6](#).

Table 6 Recommended Management Guidelines for Adverse Events Associated with Cytokine Release

Toxicity	NCI CTCAE Grade or Severity	Treatment	Modification for Subsequent infusions
Hypotension	1 Mild	
 Supportive care 	
 Increase pretreatment IV fluids (e.g., 500 ml - 1L normal saline)
Fever, Constitutional symptoms	1	
 Supportive care 	
 No modification
Hypotension	2 Moderate	
 Fluids and 1 dose of pressor (e.g. 0.3 mg epinephrine IM) Increase monitoring of vital signs If hypotension persist for more than one hour consider low dose corticosteroids (e.g. hydrocortisone 100 mg IV over 30 seconds) 	
 Extend infusion time to 2 hours. Increase pretreatment IV fluids (e.g. 500 ml -1L normal saline) Incorporate Glucocorticoid- Hydrocortisone or equivalent- 50 mg, IV, as premedication
All other cytokine release symptoms (e.g. chills, rigors, fever, nausea, vomiting)	2	
 Appropriate supportive care measure 	
 Extend infusion time to 2 hours. Consider increasing doses of prophylactic medications
Hypotension	3 Severe	
 Fluids, high dose pressors (e.g. Dopamine 10 µg/kg/min) +1 dose tocilizumab*(4mg/kg over 1 hour) If hypotension worsens or is unresponsive to above measures, administer corticosteroids If the patient’s condition does not improve or stabilize within 24 hours of the tocilizumab dose, administration of a second dose of tocilizumab +/- corticosteroids should be considered. 	
 Discuss with Sponsor

Toxicity	NCI CTCAE Grade or Severity	Treatment	Modification for Subsequent infusions
All other cytokine release symptoms (e.g. chills, rigors, fever, nausea, vomiting)	3	
 • Appropriate supportive care measures 	
 • Extend infusion time to 2 hours. • Consider increasing doses of prophylactic dose of NSAID, or antiemetic as appropriate
Hypotension/Organ toxicity, mechanical ventilation	4 Life threatening	
 • Vigilant supportive care • Fluids, • High dose pressors, • Tocilizumab (4mg/kg over 1 hour) +/- corticosteroids (hydrocortisone 100 mg IV infused over 30 seconds administered every 2 hours until symptoms resolve to <Grade 1) 	
 • Permanently discontinue

* Tocilizumab is a humanized, immunoglobulin G1k (IgG1k) anti-human IL-6R mAb approved for treatment of adult patients with moderately to severely active rheumatoid arthritis (RA) who have had an inadequate response to Disease-Modifying Anti-Rheumatic Drugs (DMARDs), for the treatment of active polyarticular juvenile idiopathic arthritis (PJIA), and active systemic juvenile idiopathic arthritis (SJIA) in patients 2 years of age and older. Tocilizumab works by preventing IL-6 binding to both cell-associated and soluble IL-6Rs. Although, it is not indicated for the treatment of cytokine release symptoms emerging clinical experience at several institutions has concluded that tocilizumab is an effective treatment for severe or life-threatening cytokine release symptoms.[19-22]

5.6.2 Nausea/vomiting

Nausea and vomiting should be treated aggressively. In addition to the prophylactic antiemetic therapy subjects receive prior to each infusion, consideration should be given to subsequent administration of antiemetic therapy every 8 hours, as needed according to standard institutional practice. Subjects should also be strongly encouraged to maintain liberal oral fluid intake.

5.6.3 Infusion Reaction

While there is some overlap between infusion reactions symptoms and cytokine release symptoms, infusion reactions symptoms, typically occur during the infusion, while cytokine release symptoms typically occur after the infusion and are mediated by a different mechanism of action. Signs/symptoms of infusion reactions may include: allergic reaction/ hypersensitivity (including drug fever); arthralgia (joint pain); bronchospasm; cough; dizziness; dyspnea (shortness of breath); fatigue (asthenia, lethargy, malaise); headache; hypertension; hypotension; myalgia (muscle pain); nausea; pruritic/itching; rash/ desquamation; rigors/chills; sweating (diaphoresis); tachycardia; tumor pain (onset or exacerbation of tumor pain due to treatment); urticaria (hives, welts, wheals); and vomiting. [Table 7](#) below shows the management guidelines for subjects who experience an infusion reaction associated with administration of the study treatment.

Table 7 Management Guidelines for Infusion Reactions

NCI CTCAE Grade	Treatment

Grade 1 Mild reaction; infusion interruption not indicated; intervention not indicated
	
Increase monitoring of vital signs as medically indicated until the subject is deemed medically stable in the opinion of the investigator.

Grade 2 Requires infusion interruption but responds promptly to symptomatic treatment (e.g., antihistamines, NSAIDS, narcotics, IV fluids); prophylactic medications indicated for ≤ 24 hrs.
	
 1. Stop Infusion and monitor symptoms. Additional appropriate medical therapy may include but is not limited to: 
 IV fluids Antihistamines NSAIDS Acetaminophen Narcotics 2. Increase monitoring of vital signs as medically indicated until the subject is deemed medically stable in the opinion of the investigator. If symptoms resolve within one hour of stopping drug infusion, the infusion may be restarted at 50% of the original infusion rate (e.g. from 100 mL/hr to 50 mL/hr). Otherwise dosing will be held until symptoms resolve and the subject should be premedicated for the next scheduled dose.

Grades 3 or 4
 
Grade 3: Prolonged (i.e., not rapidly responsive to symptomatic medication and/or brief interruption of infusion); recurrence of symptoms following initial improvement; hospitalization indicated for other clinical sequelae (e.g., renal impairment, pulmonary infiltrates)
 
Grade 4: Life-threatening; pressor or ventilatory support indicated
	
 1. Stop Infusion. Additional appropriate medical therapy may include but is not limited to: 
 IV fluids Antihistamines NSAIDS Acetaminophen Narcotics Oxygen Pressors Corticosteroids Epinephrine 2. Increase monitoring of vital signs as medically indicated until the subject is deemed medically stable in the opinion of the Investigator. 3. Hospitalization may be indicated. 4. Subjects who experience a Grade 4 reaction should be permanently discontinued from study. Subjects who experience a grade 3 reaction may be discontinued. Discussion with the Sponsor is recommended

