4.2.4 Study Stopping Rules

Rules for temporary suspension of study for death due to non-progressive disease, hematologic and non-hematologic events related to ADXS11-001 treatment

The Advaxis medical monitor and Project Manager as well as other key personnel associated with the trial (e.g. CRO Medical Monitor, Primary Investigator), as appropriate, will monitor death due to non-progressive disease and hematologic and non-hematologic toxicities for individual subjects in real-time and trial-level cumulative toxicities on a monthly basis. These events must be deemed by the Investigator at the site to have some degree of “relatedness” to ADVXS11-011 treatment (e.g. definitely, probably or possibly related) in order to be considered for evaluation. The assessment of cumulative trial-level toxicities will not begin until at least 5 subjects have received a dose of ADXS11-001 and evaluated for death and individual toxicity events following the completion of the initial 3-week treatment period. The guidelines below will be used to determine the threshold of cumulative events that will result in temporary suspension of enrollment for new subjects and dosing for any active subject until a thorough of the cumulative information is evaluated and a risk/benefit assessment conducted.

- Death (other than death related to disease progression) that occurs within 30 days of the ADXS11-001 infusion
-

- >30% Grade 3 or greater non-hematologic adverse events that are at least possibly related to ADXS11-001
- >30% Grade 4 or greater hematologic adverse events that are at least possibly related to ADXS11-001

The assessment of an individual subject event which meets the criteria as defined above and has been determined by the investigator to be related to ADXS11-001 treatment will begin as soon as all required and relevant information is received. The same project team personnel will review all of the information and determine an appropriate course of action (e.g., temporarily suspending enrollment and ongoing treatment in active subjects; temporarily suspending enrollment and allowing treatment in active subjects to continue) based on a thorough review pertaining to the event.

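### Hypotension treated with one pressor dose is Grade 2 in Table 6 but fits Grade 4 in Table 7, and no rule says which table governs an event that could belong to either

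*Combined protocol and SAP*

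**What the plan says.** Table 6 (Section 5.6.1) covers cytokine release symptoms and grades hypotension in steps.

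- **Grade 2:** the treatment is "Fluids and 1 dose of pressor (e.g. 0.3 mg epinephrine IM"; for later infusions the changes include "Extend infusion time to 2 hours", more pretreatment fluid and a steroid premedication.
- **Grade 3:** the treatment begins "Fluids, high dose pressors"; later infusions are a matter for discussion with the sponsor.
- **Grade 4:** permanent discontinuation.

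Table 7 (Section 5.6.3) covers infusion reactions. Grade 4 is "Life-threatening; pressor or ventilatory support indicated", and "Subjects who experience a Grade 4 reaction should be permanently discontinued from study". A Grade 3 reaction may lead to discontinuation, with sponsor discussion recommended.

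The grade column in each table refers to NCI CTCAE. Section 5.6.3 opens with "While there is some overlap between infusion reactions symptoms and cytokine release symptoms" and distinguishes the two by timing (infusion reactions "typically occur during the infusion, while cytokine release symptoms typically occur after the infusion") and by mechanism. Hypotension is named as a sign of both syndromes.

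Section 4.2.4 suspends enrolment and dosing at ">30% Grade 3 or greater non-hematologic adverse events that are at least possibly related to ADXS11-001". It exempts neither syndrome.

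**The concern.** A site that follows Table 6 for Grade 2 hypotension gives a pressor. Under Table 7, an indication for pressor support is part of the Grade 4 description. When the event could be called either a cytokine release symptom or an infusion reaction, the protocol gives two grades and two opposite dosing consequences, with no rule for choosing between them.

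Two things are at stake. One is the subject: continued treatment with modified infusions, or permanent discontinuation. The other is the safety signal: the suspension rule starts at Grade 3, so the same event is invisible to it under one label and counted under the other. Section 8.4 provides no external monitoring committee, so the internal reviewers depend on grades meaning the same thing at every site.

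**Working it through.** There is no stated figure to reproduce, so the check is mainly a comparison of text.

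**Step 1. The same event under each table**

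| Hypotension managed with | Table 6 | Table 7 | Counts as Grade 3 or greater? |
|---|---|---|---|
| One pressor dose | Grade 2; continue with modified infusions | Grade 4 if pressor support is taken as indicated; permanent discontinuation | Table 6 no, Table 7 yes |
| High-dose pressors | Grade 3; discuss with sponsor | Grade 4; permanent discontinuation | Yes under both |
| Life-threatening | Grade 4; permanent discontinuation | Grade 4; permanent discontinuation | Yes under both |

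Only the first row crosses the suspension threshold. The second row differs in dosing consequence but not in whether it counts. The third row agrees.

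**Step 2. Which events could fall under either table**

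Sections 4.2.2.1, 5.2.1.2 and 5.2.4 place cytokine release symptoms typically or usually 2 to 4 hours after infusion. Section 5.6.3 places infusion reactions typically during it. Most events will sort themselves. The open window is atypical timing, such as hypotension close to the end of an infusion. Mechanism is the other separator, but the protocol gives no test by which a site could apply it.

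**Step 3. Effect on the suspension rule**

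Inputs: the 30% threshold and the start of cumulative review once at least 5 subjects have been dosed and evaluated (Section 4.2.4); stage sizes of 31 and 55 in total (Section 8.2). The rule gives no denominator; I assume dosed subjects. The trigger is the smallest k with k/n > 0.30.

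| n | One short of trigger | Trigger |
|---|---|---|
| 5 | 1/5 = 20.0% | 2/5 = 40.0% |
| 31 | 9/31 = 29.0% | 10/31 = 32.3% |
| 55 | 16/55 = 29.1% | 17/55 = 30.9% |

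One reclassified event moves the proportion by 1/5 = 20 percentage points at n = 5, by 1/31 = 3.2 at n = 31 and by 1/55 = 1.8 at n = 55. It does so only if that subject has no other qualifying event.

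**Step 4. How often**

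Section 5.6.1 puts Grade 3-4 hypotension at about 1%. That implies 31 × 0.01 = 0.31 expected events in Stage 1 and 55 × 0.01 = 0.55 overall; the chance of at least one is 1 − 0.99^31 = 26.8% and 1 − 0.99^55 = 42.5%. This does not answer the question, because the affected events are Grade 2 under Table 6 and the documents give no rate for them.

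**The case against.** The best defence is that these are two syndromes, handled separately on purpose. They differ in mechanism and usual timing, and Table 5 also sets cytokine release symptoms apart from other non-hematologic toxicity. Different scales for different syndromes are not in themselves a contradiction. That stands, and it confines the point to events that could fit either table. A reader might infer that timing is the only separator, or that the tables clash throughout; Section 5.6.3 supports neither reading.

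A reader might also infer that Table 6 puts all pressor-treated hypotension at Grade 2. It does not: high-dose pressors appear at Grade 3.

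Table 7 can be read less strictly. Its Grade 4 description begins with a life-threatening qualifier, and the shared Grade 3 and 4 row lists pressors and epinephrine as separate possible therapies, so pressor use need not always mean Grade 4. This is fair, but it shows that sites can reasonably read the row differently. Table 6 itself gives intramuscular epinephrine as an example of a pressor.

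Finally, both tables are management guidance, pressor use in Table 6 is a treatment and not a grade definition, and Section 7.2.4 has a qualified physician grade every event by CTCAE. This carries some weight. Yet both tables label their grades as CTCAE, so that instruction alone does not say which description applies. Real-time medical monitoring under Section 4.2.4 may catch some divergence but supplies no assignment rule.

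**Conclusion.** The point holds in a narrow form. Hypotension treated with one pressor dose, in circumstances that fit either syndrome, can be Grade 2 with continued treatment or Grade 4 with permanent discontinuation, and can be left out of or counted towards the suspension rule. High-dose-pressor hypotension counts under either table, but its dosing consequence still differs.

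The frequency is unknown, and at the stated rate of severe hypotension few events may be involved. A reader might infer from the trigger counts that the suspension rule is materially distorted. The documents do not show that: the counts rest on an assumed denominator of dosed subjects, and no event rate is available. What can be said is that a single label could decide the outcome when the count is one short of the trigger, and that its leverage is greatest when cumulative review begins.

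This is more than missing detail, since two stated safety rules give different answers for one event. I do not judge which clinical rule is right.

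**What to change.** Reconcile Section 5.6.3 and Tables 6 and 7 in three respects:

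1. State which table governs hypotension that fits both syndromes, including events around the end of infusion.
2. Align the pressor wording so that such an event has one grade and one dosing consequence, and make clear whether a single pressor dose is pressor support in the sense of Table 7.
3. State in Sections 4.2.4 and 8.5 that the single recorded CTCAE grade feeds both the suspension rule and the adverse event tables.

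The sponsor's clinicians decide the content of the first two items. The cost is a wording amendment and notice to sites; sample size, endpoints and efficacy analyses are untouched.

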5.6.3.1 Listeriosis and Listeria Infection - Identification and Management

A person with (wt) listeriosis usually presents with fever and muscle aches, sometimes preceded by diarrhea or other gastrointestinal symptoms. Almost everyone who is diagnosed with listeriosis has an "invasive" infection, in which the bacteria spread beyond the gastrointestinal tract. The symptoms vary with the infected person. Pregnant women typically experience fever and other non-specific symptoms, such as fatigue and aches. However, infections during pregnancy can lead to miscarriage, stillbirth, premature delivery, or life-threatening infection of the newborn. In people other than pregnant women, symptoms can include headache, stiff neck, confusion, loss of balance, and convulsions in addition to fever and muscle aches. Listeriosis can present in different ways. In older adults and people with immunocompromising conditions, septicemia and meningitis are the most common clinical presentations.[23] Subjects may need immediate evaluation with a brain CT scan or MRI and a lumbar puncture with the analysis of spinal fluid to rule out meningitis.

For symptomatic patients, diagnosis is confirmed only after isolation of *Lm* from a normally sterile site, such as blood or spinal fluid (in the setting of nervous system involvement), or amniotic fluid/placenta (in the setting of pregnancy). Stool samples are of limited use and are not recommended. *Listeria monocytogenes* can be isolated readily on routine media, but care must be taken to distinguish this organism from other Gram-positive rods, particularly diphtheroids. Selective enrichment media improve rates of isolation from contaminated specimens. You can expect that the cultures will take approximately 1-2 days for growth. Importantly, a negative culture does not rule out infection in the presence of strong clinical suspicion. Serological tests are unreliable, and not recommended at the present time.[23]

Listeriosis is treated with a wide range of antibiotics. In preclinical studies, wt-*Lm* and ADXS11-001 are susceptible to the lowest tested concentration of the following antimicrobial agents:

5.6.4 Management and Surveillance of Listeria During Study Participation

A subject who experiences a fever (CTCAE Grade 1 or greater) 24 hours following the completion of ADXS11-001 infusion should be started on NSAIDs, hydration and other appropriate measures to treat the fever. In the event that the fever persists or worsens 48 hours following the completion of ADXS11-001 infusion then oral or broad spectrum IV antibiotics should be considered based on the subject's medical condition. If the fever remains unresponsive to oral/IV antibiotics 72 hours following the completion of the infusion then a blood culture should be obtained to evaluate for listeremia and determine the appropriate treatment course for the subject.

All subjects will receive a 6 month course of an oral antibiotic regimen as a prophylactic measure approximately 72 hours following the completion of the last dose of ADXS11-001 treatment or at the time of study discontinuation. This additional safety measure is intended to eradicate *Lm* from the body.

Lm surveillance monitoring will also be initiated following the completion of the last dose of ADXS11-001 treatment or at the time of study discontinuation. This monitoring will include obtaining a blood sample for CBC, CMP, including CRP and ESR, and blood cultures for the detection of listeria. Testing will be performed on all subjects who have received at least one dose of ADXS11-001 and occur every 4 months (± 2 weeks) for 3 years.

Should a diagnosis of listeriosis occur at any point after treatment with ADXS11-001 is completed immediate, intensive IV antibiotic treatment (e.g. Ampicillin +/- Gentamicin or other IV antibiotic regimen as indicated) is required. An infectious disease consult should be obtained. Based on each individual subject's case and at the discretion of the treating physician, the removal of any foreign medical object that has been present since treatment with ADXS11-001 was initiated may be warranted. It is extremely important that the investigator, his/her research staff, other healthcare providers involved in the care of the subject as well as each subject participating in this study are educated and made aware of the signs and symptoms of listeriosis and the potential for delayed listeremia/listeriosis. Educational materials for the investigator, research staff, health care providers and patients will be prepared and educational training performed.

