(1) During Study Treatment Phase - All subjects will receive a 7 day course of oral antibiotic therapy starting approximately 72 hours (Day 4) after administration of ADXS11-001. Antibiotic therapy should consist of either 160 mg trimethoprim/800 mg sulfamethoxazole (DS) tablet administered three times during the 7 consecutive days or 80 mg trimethoprim/400 mg sulfamethoxazole administered daily for 7 consecutive days or for subjects with sulfa allergies, ampicillin 500 mg four times daily for 7 consecutive days. ADXS11-001 is resistant to both streptomycin and chloramphenicol. In the event a subject experiences a persistent fever present at 72 hours after receiving ADXS11-001, the oral regimen will be replaced by broad spectrum IV antibiotics administration- until a blood culture is obtained and results are available. At this time, a specific IV antibiotic regimen may be prescribed based on the results of the blood culture. Should a diagnosis of listeriosis be made intensive IV antibiotic treatment must be initiated. Ampicillin +/- Gentamicin is the preferred treatment regimen but other IV antibiotics may be used based on the subject's tolerance, culture and sensitivity results. An ID consult should be obtained.

(2) Post Study Treatment - All subjects will receive a 6 month course of oral trimethoprim/sulfamethoxazole or ampicillin for subjects with sulfa allergies to be initiated approximately 72 hours following the last dose of study treatment or at the time of study discontinuation. Trimethoprim/sulfamethoxazole therapy should consist of either 160 mg trimethoprim/800 mg sulfamethoxazole (DS) tablet administered three times a week or 80 mg trimethoprim/400 mg sulfamethoxazole administered daily for 7 consecutive days. The dose of ampicillin consists of 500 mg four times daily for 6 months.

Tumor Imaging/Disease Assessment - CT scan or MRI for determination of unidimensional measurements and disease response. Imaging studies and tumor assessments will be performed every 9 weeks starting at Week 8 of Cycle 1.

Pregnancy test - A rapid pregnancy test will be performed within 72 hours of each treatment administration (combination or monotherapy) for all women of child bearing potential prior to treatment. A positive rapid pregnancy test must be confirmed, prior to dosing, by a serum pregnancy test (minimum sensitivity 25 IU/L or equivalent units of β HCG).

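### For fever persisting at 72 hours after infusion, Sections 5.6.4 and 7.1.6.2 disagree on the antibiotic route and on what triggers the blood culture

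*Combined protocol and SAP*

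**What the plan says.** Section 5.6.4 (Management and Surveillance of Listeria During Study Participation) sets out three steps, timed from the end of the infusion.

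- At 24 hours, a subject with fever "24 hours following the completion of ADXS11-001 infusion should be started on NSAIDs, hydration and other appropriate measures to treat the fever". No antibiotic is mentioned.
- At 48 hours, the condition for the next step is: "the fever persists or worsens 48 hours following the completion of ADXS11-001 infusion". The response to it is discretionary and depends on the subject's condition: "then oral or broad spectrum IV antibiotics should be considered".
- At 72 hours: "If the fever remains unresponsive to oral/IV antibiotics 72 hours following the completion of the infusion then a blood culture should be obtained". The culture is to look for listeremia and guide further treatment.

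Section 7.1.6.2 (Treatment Period), in its instructions on prophylactic antibiotics, first gives a rule for everyone: "All subjects will receive a 7 day course of oral antibiotic therapy starting approximately 72 hours (Day 4) after administration of ADXS11-001". It then turns to fever and sets the trigger: "In the event a subject experiences a persistent fever present at 72 hours after receiving ADXS11-001". What follows for such a subject is that "the oral regimen will be replaced by broad spectrum IV antibiotics administration". The IV treatment runs until a culture has been taken and its results are known, when a specific IV regimen may be chosen.

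Both texts are current. The Summary of Changes lists them as additions in the same revision (items 22 and 28), so neither supersedes the other.

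**The concern.** A site treating a subject who is still febrile at 72 hours may turn to either section in good faith. Section 5.6.4 carries the title on Listeria management, while Section 5.2.5 sends readers to Section 7.1.6.2 for details of the antibiotic regimen. One section leaves the route open and makes the culture depend on failed antibiotics. The other calls for IV treatment and assumes a culture for any persistent fever at that hour.

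What is at stake is consistent handling of a possible infection with the live vector. By the protocol's own account, the vector is highly sensitive to antibiotics (Section 4.2.2), and in symptomatic patients listeriosis is confirmed only by isolating the organism from a normally sterile site such as blood (Section 5.6.3.1). Whether a culture is triggered, and how much antibiotic comes before it, can therefore affect whether an infection is found in an individual subject.

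**Working it through.** No sample size, error rate or event count is involved, so the check is a side-by-side reading.

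| Item | Section 5.6.4 | Section 7.1.6.2 |
|---|---|---|
| Clock | From completion of the infusion | From receiving the product |
| Fever step at 48 h | Oral or IV antibiotics, discretionary | None |
| Routine oral course | Not part of the fever steps | About 72 h, all subjects, febrile or not |
| Trigger at 72 h | Fever unresponsive to antibiotics | Persistent fever; no condition on earlier antibiotics |
| Route at 72 h | No instruction; the culture guides treatment | IV in place of oral |
| Culture | At 72 h, if the trigger is met | Tied to the 72 h fever; no separate time |
| Reference to the other fever rule | None | None |

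Now apply both sections to the subjects they could cover.

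1. **Febrile at 48 h, given no antibiotic, still febrile at 72 h.** Section 5.6.4 permits the absence of antibiotics, because the 48-hour step is discretionary. At 72 h the fever cannot be called unresponsive to a treatment not given, so on a literal reading no culture is triggered, and no IV step is ordered. Section 7.1.6.2 covers this subject with IV treatment and a culture. The sections differ on both points.
2. **Given oral antibiotics at 48 h, still febrile at 72 h.** Section 5.6.4 calls for a culture and is silent on route while the result is awaited. Section 7.1.6.2 calls for IV in that interval. The sections differ on route. The oral regimen named in Section 7.1.6.2 is also the routine course, which is only due to begin at about that hour; the section does not say how it relates to oral treatment begun at 48 h.
3. **Given IV antibiotics at 48 h, still febrile at 72 h.** Both sections lead to a culture with IV treatment in place. There is no material difference.
4. **Fever resolved before 72 h.** Only the 48-hour step of Section 5.6.4 applies. There is no conflict.

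The mismatch therefore lies in cases 1 and 2. In neither section is it stated whether the culture is drawn before IV treatment starts. The difference between the clocks is minor: if the second runs from the start of infusion, it equals the infusion time.

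**The case against.** The strongest reply is that a site can obey both sections: consider antibiotics at 48 hours, then at 72 hours take a culture and give IV treatment until the result is known. Neither section forbids what the other requires. Section 5.6 is also framed as supportive care guidance applied at the investigator's judgement. This stands to the extent that the texts are not logically incompatible. It does not remove the mismatch, because a site that follows Section 5.6.4 alone can keep a subject on oral treatment, or take no culture, and so depart from Section 7.1.6.2 without any signal that it has done so.

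Two stronger readings are tempting, and the documents do not support them.

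- *A reader might infer that the sections contradict each other on when antibiotics start, by 72 − 48 = 24 hours.* The course at about 72 hours is routine prophylaxis for every subject, and the 48-hour step is an optional response to fever. They can follow one another.
- *A reader might infer that they contradict each other on when the culture is taken.* Both attach it to the fever at 72 hours. What differs is the condition that triggers it.

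The reply can add that few subjects are likely to be involved. The protocol describes cytokine-release symptoms, fever among them, as typically resolving within 12 to 24 hours (Section 4.2.2.1; similarly Section 5.2.4). That suggests that treatment-related fever at 72 hours is uncommon, though the documents give no rate.

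**Conclusion.** The point holds in a limited form. For persistent fever at 72 hours, the two sections differ on route (no IV step against replacement of oral by IV) and on the culture trigger (failure of antibiotics that were optional, against persistent fever alone). The differently worded clocks and the missing cross-reference add to this.

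Its size cannot be put as a number, because the documents give no frequency for fever lasting to 72 hours. It concerns only subjects still febrile at that time, not everyone with a fever between 48 and 72 hours.

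A reader might also infer that listeremia detection becomes non-comparable across sites and that a trial outcome is damaged. The documents do not support that. The Listeria surveillance listed among the safety criteria in the Section 1 Summary is the post-treatment testing every 4 months for 3 years, not cultures for acute fever. Section 8.5 plans no listeremia analysis and no comparison of sites. Sample size, error rates and the planned efficacy and safety analyses are unaffected. The conclusion rests on a literal reading of the 72-hour condition in Section 5.6.4; a site that reads it loosely would take the culture anyway, but the difference on route would remain.

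**What to change.** The sponsor's clinical team should reconcile Sections 5.6.4 and 7.1.6.2 into a single sequence for persistent fever. It should settle:

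- the clock from which the hours are counted;
- the condition that triggers the blood culture, including for a subject who has had no antibiotic;
- the antibiotic route while results are awaited, and how it relates to the routine 7-day oral course;
- the order of culture and antibiotics.

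State the sequence in one section and cross-refer to it from the other. Which sequence is intended is a clinical decision for the sponsor. The cost is protocol wording, a notice to sites, and agreement with the educational material that Section 5.6.4 already promises. No change to the statistical plan is needed.
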